6.2 Study Groups

Historical Control Group (Group 1): The historical control group will consist of up to 80 mechanically ventilated patients with documented presence of one or more chronic cardiac or pulmonary conditions that underwent planned extubation during the study period and meet all inclusion criteria outlined below.

Interventional Group (Group 2): The interventional group will consist of up to 40 patients for whom the LAR provides informed consent and who meet all study eligibility criteria.

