6.3 Participant Identification Procedures and Eligibility Criteria

6.3.1 Historical Control Group:

Reintubation rates are tracked at the institutional level as part of quality assessments; a delegated member of the study team will utilize this patient list to generate a study-specific subset of high-risk patients who were mechanically ventilated between February and October 2019. This list will be screened for the inclusion/exclusion criteria below by a delegated member of the study team. The study statistician or designee will then use a random number generator to generate a final group of 80 patients that meet inclusion criteria.

Inclusion Criteria

1. Age ≥ 18 years
2. Chronic cardiac or pulmonary condition
 - o COPD, history of based on any documentation notes
 - o CHF, history of based on any documentation notes
 - o Positive fluid balance, defined as a positive number when calculating fluid input minus fluid output over the approximate 24-hour-period prior to extubation
3. Documented modified RSBI between 58-105 on the day of extubation

Exclusion Criteria

1. Patients receiving comfort care or terminal extubation
2. Home ventilator, based on any documentation notes
3. Only primary extubations will be included (i.e., if the patient list query identifies multiple mechanical ventilations, only the primary encounter/event will be included)

6.3.2 Prospective Group:

An EMR-based report of all patients that have been on mechanical ventilation (MV) at Grant Medical Center for at least 24 hours will be generated daily (Monday through Friday), per standard procedure. Eligibility determination for this cohort will be conducted by a delegated member of the study team across two time points: pre-screening to determine eligibility to approach for consent, and eligibility on the day of extubation to determine enrollment eligibility (Appendix A). Only patients meeting all required eligibility criteria above will be enrolled to the study; any PHI collected for patients that are not subsequently enrolled will be destroyed after non-eligibility determination.

Pre-Screening Criteria:

1. No home ventilator, based on any documentation notes
2. Not scheduled for terminal extubation/comfort care
3. Has not had a failed extubation during the current hospital stay
4. Has not previously participated in the current trial

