5. Any other reason, at the discretion of the study team/clinical care staff, that should preclude the LARs being approached. These include, but are not limited to, facial trauma or other severe injuries that make extubation unlikely or that would make BiPAP contraindicated. Because patients will be screened daily, it is possible that a patient that fails pre-screening earlier in the stay may be eligible for enrollment later in their stay. This is okay.

Day of Extubation Criteria

1. Patient/LAR provided informed consent
2. Documented high-risk factors of interest (CHF, COPD, and/or positive fluid balance) as defined for the historical control cohort
3. The modified RSBI must be between 58-105
4. Patient must successfully complete spontaneous breathing trial and be determined eligible for extubation
5. Patient must not have extubated themselves
6. The patient must have no other contraindication that would preclude the postextubation protocol (e.g., facial trauma, tracheotomy, or any other reason that would preclude use of BiPAP or HFNC)
7. The patient must not be undergoing terminal extubation or placed on comfort care

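### Minor: Section 6.3.1 does not hold the historical controls to two entry conditions of the prospective group, at least 24 hours of ventilation and no contraindication to BiPAP/HFNC

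*Combined protocol and SAP*

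**What the plan says.** Section 6.3.2 starts prospective screening from "An EMR-based report of all patients that have been on mechanical ventilation (MV) at Grant Medical Center for at least 24 hours", run Monday to Friday. The 24-hour condition is not a numbered criterion, but this report is the only route into the group that the section describes. Prospective patients are then screened twice for suitability for the devices. Pre-screening item 5 names "facial trauma or other severe injuries that make extubation unlikely or that would make BiPAP contraindicated". Day-of-extubation item 6 says "The patient must have no other contraindication that would preclude the postextubation protocol", with facial trauma and tracheotomy as examples.

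Controls come from an institutional quality list for February to October 2019. Section 6.3.1 says "This list will be screened for the inclusion/exclusion criteria below by a delegated member of the study team", after which the statistician will "use a random number generator to generate a final group of 80 patients that meet inclusion criteria". Section 6.2 describes controls as patients who "underwent planned extubation during the study period and meet all inclusion criteria outlined below".

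The plan does align the groups on risk. The day-of-extubation criteria require "Documented high-risk factors of interest (CHF, COPD, and/or positive fluid balance) as defined for the historical control cohort", and the modified RSBI range is the same in both groups.

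**The concern.** With a historical control group, comparability rests on applying the same entry rules to both groups wherever a chart allows it. Here two rules that decide who can enter the prospective group are not applied to the controls, and no reason is given. Controls may therefore include patients ventilated for less than a day, or patients who could not have been given the study protocol. Neither kind can appear in the prospective group.

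Two comparisons are exposed. Ventilator time is a secondary outcome, and the 24-hour condition acts on it directly. The 72-hour reintubation contrast is the primary analysis, and its control rate is also meant to inform a later randomized trial (Section 3.1).

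**Working it through.** **1. Entry rules side by side.**

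| Rule | Prospective (6.3.2) | Controls (5, 6.2, 6.3.1) |
|---|---|---|
| COPD, CHF or positive fluid balance | yes | yes |
| Modified RSBI 58-105 | yes | yes |
| No home ventilator | yes | yes |
| Planned extubation | yes (SBT passed, no self-extubation) | yes |
| First extubation only | yes (no earlier failure in the stay) | yes |
| No comfort care or terminal extubation | yes | yes |
| Ventilated at least 24 h | yes, through the report | not stated |
| No BiPAP/HFNC contraindication | yes, twice | not stated |

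Planned extubation already removes controls whose injuries made extubation unlikely, and most tracheotomy cases. What remains of the last row is mainly charted facial trauma and other charted reasons against BiPAP or HFNC. The random draw follows screening, so it prevents hand-picking but does not change who is eligible.

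**2. Does the planned adjustment close the gap?** Section 7.1.1 adds only baseline characteristics that differ significantly. The plan defines no variable for either rule. Suppose each were coded yes/no. With x of 80 controls and 0 of 40 prospective patients affected, the smallest expected count is x × 40/120 = x/3, which is below 5 for x < 15, so Section 7.1 calls for Fisher's exact test. It gives p = 0.0508 at x = 8 and p = 0.028 at x = 9. Up to 8 of 80 controls (10%) could then be affected without the item entering the model. With X ~ Bin(80, f), P(X ≥ 9) is below 0.1%, 1.8% and 40.7% at assumed f = 2%, 5% and 10%. Entry is therefore not reliable.

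**3. Ventilator time.** Section 7.1.2 uses an unadjusted Wilcoxon test. Assume that a share f of controls has total time under 24 h and that there is no other difference. The chance that a prospective value exceeds a control value is f + (1 − f)/2 = 0.5 + f/2. The null SD of that estimate is √[121/(12 × 40 × 80)] = 0.0561. The standardized shift is (f/2)/0.0561 = 0.18, 0.45 and 0.89 at f = 2%, 5% and 10%. The normal approximation Φ(−1.96 + shift) + Φ(−1.96 − shift) gives 5.4%, 7.3% and 14.5% rejection. Simulation with 60,000 trials per share and a continuity correction gave 4.9% at f = 0, then 5.1%, 6.8% and 13.3%. A run of 40,000 trials gave 5.2%, 7.1% and 13.7%.

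**4. Reintubation.** The shift in the control rate is share × rate gap. All inputs are assumed.
- Under 24 h, share 2-10%, rate 5-15 points lower: 0.02 × 5 = 0.1 to 0.10 × 15 = 1.5 points lower.
- Contraindicated, share 2-10%, rate 10 points higher or lower: 0.2 to 1.0 points either way.
- Both at their extremes in the same direction: 1.5 + 1.0 = 2.5 points.

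For scale, at an assumed 20% rate (Section 3.2 cites 19% and 23% from a trial in high-risk patients), the 95% half-width for 40 v 80 is 1.96 × √[0.16 × (1/40 + 1/80)] = 15.2 points.

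More extreme inputs give more. With 30% of controls affected and a rate of 35% in the others, rates of 2 or 0.25 times that shift the control rate by 0.30 × 35 = +10.5 or 0.30 × 0.75 × 35 = −7.9 points. The documents give no share at all, and planned extubation makes 30% hard to credit for the contraindication rule.

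**The case against.** The best case against the point is that this is a declared exploratory, non-randomized pilot, every share above is assumed, and the reintubation shift is lost in the sampling error. The institutional list may already have a ventilation threshold, and Appendices A and F, known only by title, may capture these items. Much of the contraindication rule is bedside discretion that no chart review can reproduce. All of this stands, and it is why the point is minor. It does not remove the difference in the written rules, or the one-sided cut in ventilator time if the list has no threshold.

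Four stronger readings are tempting and are not supported.
- A reader might infer that the control exclusion "Patients receiving comfort care or terminal extubation" drops patients who moved to comfort care after a failed extubation. It sits in a list about the index extubation and beside terminal extubation, so status at extubation is the natural meaning.
- A reader might infer that adjustment is impossible because no prospective patient falls in the affected strata. In a model with group and an indicator for such a stratum, the group coefficient is the same as if those controls were dropped. The weakness is that the item may never enter, and even the 9-of-80 threshold assumes a yes/no coding. Ventilation time kept continuous would be tested differently.
- A reader might infer a reintubation bias in favour of the protocol. The two rules can pull in opposite directions.
- A reader might take the 3-5 days in Section 6.4 as the control distribution and derive the share under 24 h. That section covers the prospective group only and may already describe patients past 24 h.

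**Conclusion.** The gap in the text is certain: Section 6.3.1 lacks both conditions, and no other section supplies them. Its effect is modest. For ventilator time the direction is known, toward longer prospective time, provided that the institutional list has no threshold of its own. The false-rejection rate is near nominal if few controls fall under 24 h and reaches about 13-14% at an assumed 10%. For 72-hour reintubation the effect is probably small next to the sampling error, and its net direction cannot be derived. Neither Section 6.1, which names the type of oxygen management as the confound, nor Section 6.8, which names consent, covers the point. It is a minor improvement worth making because it is cheap.

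**What to change.** Before the random draw, amend Section 6.3.1 to require at least 24 hours of ventilation before the index extubation, and no charted facial trauma or other charted contraindication to BiPAP/HFNC. If the institutional list already has a ventilation threshold, stating it there settles the first part. If the controls are already drawn, record both items and repeat the primary and ventilator-time analyses on controls who meet the aligned rules.

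This does not fully mirror the Monday-to-Friday report. A patient who passes 24 hours and is extubated over a weekend might never appear on it. Either limit controls to those who would have been on a weekday report, or state the remaining difference in Section 6.8. Optionally, and as wording only, say that comfort-care or terminal status is judged as of extubation.

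The cost is a few lines of protocol text and about two chart items. The control group becomes somewhat smaller, which the limit of up to 80 permits. If each rule removes an assumed 2-10% of 80 drawn controls, 80 × 0.98² = 76.8 to 80 × 0.90² = 64.8 remain, and the half-width rises from 15.2 to 15.3-15.8 points. Contraindication read from a chart is less certain than at the bedside, and the documents do not give the size of the eligible pool.

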6.4 Recruitment and Informed Consent (Prospective Group Only)

Patients are typically on mechanical ventilation for approximately 3-5 days, allowing several days from the time of identification for recruitment and consent. Because patients will be sedated and intubated, informed consent will be obtained from the patients' legally authorized representatives (LAR). Specifically, a member of the patient's care team will give each family of mechanically ventilated patients a recruitment card (Appendix B) and explain that a member of the research team will be approaching them to discuss the study. This ensures that the LARs are introduced to the study by the patients' care team.

The LAR will sign the informed consent document prior to any procedures being done specifically for the study only (i.e. above routine care). A copy of the signed informed consent document will be given to the LAR for their records, with a copy placed in the patient's medical record. Because patients may remain sedated following extubation, it may be not practicable to re-consent all patients following extubation. Patients in the Intensive Care Unit are assessed for confusion/delirium as standard of care using the Confusion Assessment Method for the ICU (CAM-ICU). Therefore, each patient's routine CAM-ICU score will be reviewed daily by a member of the study team. Those with negative CAM-ICU scores will be informed by a member of the study team that they were enrolled in a research study by their LAR, and the patient will be provided the opportunity determine whether they wish to remain enrolled in the study using the regained capacity portion of the consent form (Appendix C). Patients with positive CAM-ICU scores or who are transferred outside of the ICU (where CAM-ICU is not conducted) will not be re-consented. It is important to note that at this time all study interventions would have been completed; patient consent can only be obtained for continued data collection. Patients who do not wish to continue will be treated as outlined in [Section 6.6](#).

All informed consent procedures (initial and in the event of regained capacity) will be obtained and documented on an IRB-approved informed consent form (Appendix C) in accordance with the OhioHealth Research Institute (OHRI) policy for obtaining and documented informed consent.

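### The 24-hour, weekday-report filter applies only to the intervention group; controls have no stated minimum ventilation time or report-day condition

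*Combined protocol and SAP*

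**What the plan says.** Section 6.3.2 describes one way of finding prospective patients: "An EMR-based report of all patients that have been on mechanical ventilation (MV) at Grant Medical Center for at least 24 hours", which "will be generated daily (Monday through Friday), per standard procedure". Consent from the legally authorized representative (LAR) must follow: "The LAR will sign the informed consent document prior to any procedures being done specifically for the study only" (Section 6.4). The same section gives the expected time scale: "Patients are typically on mechanical ventilation for approximately 3-5 days, allowing several days from the time of identification for recruitment and consent".

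Controls come from an institutional list kept for quality purposes. From it the team will "generate a study-specific subset of high-risk patients who were mechanically ventilated between February and October 2019". Then, "This list will be screened for the inclusion/exclusion criteria below by a delegated member of the study team", and the statistician will "use a random number generator to generate a final group of 80 patients that meet inclusion criteria". The criteria cover age, chronic condition or fluid balance, modified RSBI, comfort care or terminal extubation, home ventilator, and first extubation only. None concerns ventilation time or day of the week. The fluid-balance item looks back about a day before extubation, but it is only one of three alternative risk factors and does not require ventilation over that time.

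Section 7.1.1 adjusts the primary logistic model for demographic and baseline characteristics that reach statistical significance. It does not name ventilation time before extubation. Section 7.1.2 compares ventilator time between groups by an unadjusted Wilcoxon test. Section 6.8 lists one limitation: consented patients may not be representative.

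**The concern.** Aim 1 is a between-group difference in reintubation within 72 hours, and Section 3.1 says the data will be used to plan a randomized trial. If one group is filtered on ventilation time and the other is not, the groups differ by construction before any treatment is given. Part of the observed difference could then come from the sampling rule.

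The ventilator-time comparison is affected more directly. The study treatment starts only at extubation, so time on the ventilator up to that point cannot be a treatment effect. Removing the shortest courses from one group shifts that comparison whatever the protocol does.

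**Working it through.** **1. The plan's own figures (Section 5).** 4 patients per business day × 20 days = 80 per month (3 per day would give 60). 80 × 0.30 = 24 high-risk per month. 80 × 3 months = 240 consented. These reproduce, and none of them takes account of the filter.

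**2. The two frames side by side.**

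| | Prospective (6.3.2, 6.4) | Control (6.3.1) |
|---|---|---|
| Source | Electronic-record report | Quality list, February-October 2019 |
| Minimum ventilation time | 24 h | None stated |
| Days covered | Monday-Friday | Not stated |
| LAR consent needed | Yes | No |

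**3. Share of courses the report can capture.** Assumptions not in the documents: intubation times are uniform over the week, there is one report per weekday at a fixed hour, and a patient is captured if still ventilated at a report with at least 24 h elapsed. Gaps between reports are four of 24 h and one of 72 h (total 168 h). For a course of D hours the usable window is L = D − 24, and for L > 0

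capture = 1 − Σ max(0, gap − L) / 168.

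- Under 24 h: 0%
- 36 h: 1 − (4×12 + 60)/168 = 36%
- 48 h: 1 − 48/168 = 71% (29% missed)
- 72 h: 1 − 24/168 = 86% (14% missed)
- 96 h or more: 100%

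A seven-day report would raise the 36 h figure to 50% and give 100% from 48 h, but would still capture nothing under 24 h.

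**4. Effect on case mix at the stated typical 3-5 days.** With equal weights on 3, 4 and 5 days (an assumption), the 3-day share is 1/3 = 33% of controls and 0.857/(0.857 + 1 + 1) = 30% of prospective patients. Mean duration is 4.00 days against (3×0.857 + 4 + 5)/2.857 = 4.05 days.

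**5. Consent time.** If consent needs a further 24 h after the report (assumed), L = D − 48. The loss becomes 48/168 = 29% at 72 h, 24/168 = 14% at 96 h and 0% at 120 h. The 3-day share among prospective patients falls to 0.714/(0.714 + 0.857 + 1) = 28%.

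**6. What the 24-hour condition could do to Aim 1.** Suppose there is no treatment effect, a share s of controls was ventilated under 24 h, and reintubation risks are p_short and p_long. The spurious difference (intervention minus control) is s × (p_long − p_short). The documents give none of these values. With s from 10% to 40%, and assumed pairs of 5% and 20%, 12% and 19%, 12% and 23%, 14% and 35%, it runs from 0.10 × 0.07 = 0.7 to 0.40 × 0.21 = 8.4 percentage points against the intervention. If short courses carried the higher risk, the sign would reverse.

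**7. Is the control pool large enough after matching?** Section 5 expects 40 enrolled in about 12 weeks, after the report filter and consent. February to October is about 39 weeks, and 40 × 39/12 = 130, which exceeds 80. This assumes that Section 5's rate is right and that 2019 was similar.

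**The case against.** **Control coverage.** A reader might infer that controls are known to come from every day of the week. They are not. Section 6.3.1 does not say how the quality list is compiled, and Section 5 counts patients per business day. The weekday part of the point is therefore conditional.

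**Absolute exclusion.** A reader might also infer that a patient missed by the weekday report can never be enrolled. The documents do not establish this. Neither 24 h of ventilation nor a weekday is an eligibility criterion. Section 5 intends to approach all ventilated adults who pass pre-screening, Section 6.3.2 speaks of daily screening, and Section 6.4 gives a card to each family. What stands is that the report is the only identification route described, and that the card only introduces the study.

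**A larger case-mix shift.** If courses were spread equally over 1.5, 2, 3, 4 and 5 days, those of 2 days or less would be 40% of controls and (0.357 + 0.714)/3.929 = 27% of prospective patients. That mix conflicts with the stated typical 3-5 days and should not be relied on.

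**Effect on reintubation.** The risk factors listed in Section 3.2 do not include ventilation time. This stands: the documents support neither a direction nor a size.

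**Existing safeguards.** The study is exploratory, expects baseline differences and adjusts for significant ones. But ventilator time is listed as an endpoint, so it may never be screened as a baseline characteristic. If it is screened, its inclusion depends on a significance test in at most 120 patients. Seeing an imbalance in the secondary comparison does not adjust the primary one.

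**Conclusion.** The point holds, with the 24-hour condition as its firm part: an entry filter in one group with no stated counterpart in the other. It truncates ventilation time in the intervention group directly. It may also move the Aim 1 difference, by an amount and in a direction that cannot be known from the documents. The 0.7 to 8.4 point range shows only what assumed inputs would produce and is not an estimate.

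The weekday schedule is secondary. It rests on the control list covering all days and on evenly spread intubations. At 3-5 days it shifts the 3-day share only from 33% to 30%, or to 28% if consent takes another 24 h. The planned significance-based adjustment does not reliably correct either part.

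**What to change.** - **Control criteria (6.3.1).** Add: *was on the ventilator, with at least 24 hours since intubation, at one or more Monday-to-Friday report times before extubation, computed from timestamps with the report time used in 6.3.2*. State that report time, since the documents do not give it. A 24-hour minimum alone would leave the weekday gap.
- **Quality list.** State how it is compiled and whether it includes weekend extubations.
- **Primary model (7.1.1).** Pre-specify ventilation time from intubation to first extubation as a covariate whatever its p-value, and keep it distinct from the total ventilator time endpoint.
- **Limitations (6.8).** Record that LAR consent time applies to one group only and stays unmatched.

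A forced weekday/weekend term is not recommended as routine. At the 19-23% reintubation rates quoted in Section 3.2 (assumed to apply here), 120 patients give 120 × 0.19 ≈ 23 to 120 × 0.23 ≈ 28 events. If few weekend extubations are enrolled, the term would also be closely tied to group.

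The cost is one timestamp rule in a retrospective query, the loss of some short-course controls from a pool that should still exceed 80, and one model parameter. No patient procedure changes.
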